like vapor and tobacco and other flavors. Decades of research highlight the importance of sensorimotor stimuli in maintaining behavior even when nicotine is absent.^{47,48} Stimuli that have been associated with nicotine can elicit craving,⁴⁹ increase the probability of use,⁵⁰ increase positive subjective experiences,⁵¹⁻⁵⁴ reduce withdrawal,^{53,55,56} and support behavior even in the absence of the drug.^{57,58} These data suggest that the sensorimotor experience is an important determinant of whether a product will substitute for traditional cigarettes. E-cigarettes may serve this function better than other alternative products which might explain both why they were chosen most often in our pilot study (Overview D.2) and why they attenuate abstinence in cigarette users even if they do not deliver nicotine.⁴³

E-cigarettes are available in a variety of flavors that may impact the appeal and reinforcing effects of the product. The full impact of flavors on e-cigarette use is still unknown, but it seems likely that the availability of non-tobacco flavors influences the likelihood of use. Recent estimates are that 53% of adults use e-cigarettes with flavors other than tobacco.⁵⁹ Other studies also supported this assumption, demonstrating that liquid flavor choices influence appeal and choice of e-cigarette device.^{59, 60} If flavors impact the appeal of e-cigarettes, they may also impact the likelihood that smokers will switch from VLNC cigarettes to these products.

Measures for assessing product use and the impact of product characteristics

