Participants will undergo one of four marketplace conditions during Virtual Visits 2-5, with the order of administration randomized across participants.

- Marketplace Condition 1 includes moderate nicotine content vape with all flavor e-liquids.
- Marketplace Condition 2 includes moderate nicotine content vape with tobacco e-liquids.
- Marketplace Condition 3 includes low nicotine content vape with all flavor e-liquids.
- Marketplace Condition 4 includes low nicotine content vape with tobacco e-liquids.

Staff will instruct participants to complete the ETM task as if they are purchasing the products from a retailer, and that one iteration of the task will be randomly selected and will determine which products they will use during the field assessment. In reality, we will randomly assign which condition is used (Condition 2 or 4) but will assign products based on when NNC were not available to simulate a nicotine content reduction policy.

For each marketplace condition, participants will complete 7 iterations of the ETM task in ascending order. The prices for NNC cigarettes on the ETM will be set at: \$0.12, \$0.25, \$0.50, \$1.00, \$2.00 per cigarette; in the 1st ETM condition, NNC cigarettes will be set at \$0.25 with no VLNC available to purchase to simulate current market status; while in the 6th ETM condition, NNC will be eliminated from the marketplace to simulate a nicotine content reduction policy. The costs for the other products will reflect average prices in NC and will not change during the task. For each task iteration, participants will receive individually-tailored account balances approximately equal to the money they would spend on cigarettes for seven days. They can purchase as many or few products as their account balance allows. Participants are not required to buy products from the ETM or can buy nicotine gum if they prefer. If they do not buy products from the ETM and do not use tobacco products during the field assessment, then they will receive their ETM account balance at Virtual Visit 6. This payment is delayed to reduce the likelihood that they will use this money to buy their preferred brand cigarettes, thus decreasing the validity of the ETM task.

Participants will be instructed to use only the products purchased from the ETM during the subsequent 7-day period after Virtual Visit 5 and told that we will assess adherence at Lab Visit 3.

In-Person Lab Visit 2

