Raw data will be analyzed using a linear mixed-effects model that includes main effects for e-liquid nicotine content (low vs. moderate), e-liquid flavors (all vs. tobacco only), visit, price condition (analyzed as a categorical variable), and a carryover effect for the previous visits condition (treated as a four-level categorical variable, and random effects for participant and visit nested within participant. This will account for correlation from multiple observations from the same participant, both within and across visits. We will also evaluate whether there is an interaction between the e-liquid nicotine content and e-liquid flavors factors. If significant, the interaction will be included in the model; otherwise, it will be removed. The analysis of derived behavioral economic measures will follow an analogous approach, except that for each measure, there will only be a single outcome for visit. As a result, our linear mixed-effects model will not include a main effect for price condition, and there will only be a single random effect for each participant. Behavioral economic measures will be derived by generating demand curves using an exponential demand equation. Specific measures considered will include: Alpha - the rate of change in demand, and Q_0 – peak consumption. For all analyses, assessments of key model assumptions will be completed and we will consider transformations or alternate analytic approaches if these assumptions are violated.

Analysis of Secondary Outcomes

The analysis of secondary endpoints will be analogous to the analysis described above for the primary endpoints. The amount of e-liquid purchased will be analyzed both as the raw data for each price condition and using derived behavioral economic measures. The analysis of these endpoints will be completed using linear mixed-effects models with the fixed and random effects terms described above. The analysis of the various scales and scores collected at each visit will follow the same approach as the analysis of derived behavioral economic measures described above. As before, assessments of key model assumptions will be completed and we will consider transformations or alternate analytic approaches if these assumptions are violated.

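### The primary model has no ban contrast and no price-by-factor term, so it cannot show whether removing NNC cigarettes is sufficient or needs flavored or higher-nicotine e-cigarettes as well

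*Combined protocol and SAP*

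**What the plan says.** **Design (Virtual Visits 2-5).** The four marketplaces form a 2x2 of e-liquid nicotine and flavor. "Marketplace Condition 1 includes moderate nicotine content vape with all flavor e-liquids". "Marketplace Condition 2 includes moderate nicotine content vape with tobacco e-liquids". Condition 3 pairs low nicotine with the full flavor range. "Marketplace Condition 4 includes low nicotine content vape with tobacco e-liquids".

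The same task sequence runs in each: "For each marketplace condition, participants will complete 7 iterations of the ETM task in ascending order". In the first iteration NNC costs $0.25, "with no VLNC available to purchase to simulate current market status". The ban is a later iteration: "while in the 6th ETM condition, NNC will be eliminated from the marketplace to simulate a nicotine content reduction policy".

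**Question (Objectives).** The study is meant to establish whether a ban on NNC is enough to move smokers to less harmful products, or whether higher-nicotine and/or flavored alternatives are also required.

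**Analysis (Statistical analysis plan; Analysis of the Primary Outcome).** The primary objective is stated as the effect of the two e-liquid factors on purchasing. The raw-data model has main effects for nicotine, flavor, visit and carryover, and for "price condition (analyzed as a categorical variable"). The only interaction considered is nicotine by flavor. No comparison of the NNC-eliminated iteration with any reference is specified.

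**Background on the actual market.** "E-cigarettes are available in a variety of flavors that may impact the appeal and reinforcing effects of the product". The same section gives 53% of adults as users of non-tobacco e-cigarette flavors, and the paragraph on nicotine says some devices deliver at least as much nicotine as a cigarette.

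**The concern.** The question in the Objectives is about what happens when NNC disappears, and whether the answer depends on the e-liquids left on sale. In model terms that is a ban contrast and its interaction with the two factors. The written model contains neither, so the ban effect cannot differ between marketplaces, and the factor effects come mostly from iterations in which NNC is still for sale.

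The label on iteration 1 adds a second ambiguity. It is described as today's market in all four marketplaces, but flavors, moderate nicotine or both are already missing in three of them. A report that compares each ban with the current market could use each marketplace's own iteration 1 or a single status quo. These are different estimands, and the plan does not choose between them.

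The protocol's rationale gives a reason to expect interaction: it argues that better nicotine delivery helps e-cigarettes compete with the weakened reinforcement of very low nicotine content (VLNC) cigarettes. That predicts larger e-liquid effects once only VLNC cigarettes remain.

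**Working it through.** **1. Iteration count.** Five NNC prices ($0.12, $0.25, $0.50, $1.00, $2.00) + one current-market iteration + one NNC-eliminated iteration = 7, which matches the stated figure. A 6th 'ETM condition' is mentioned but there are only four marketplaces, so the term must mean iteration, and the current-market label applies in all four. With 64 completers there are 64 x 4 = 256 iteration-1 records. Only the 64 in Condition 1 (25%) have both moderate nicotine and all flavors.

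**2. What the model can represent.** I take price condition to have seven levels, since the SAP says each participant contributes all price combinations within a visit. Let L = 1 for low nicotine and T = 1 for tobacco flavor only. Let n and f be the rises in cigarette purchases from each restriction, and let p(k) be the effect of iteration k. Apart from visit and carryover, the mean is

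m + p(k) + n·L + f·T.

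- Ban minus own iteration 1: b = p(ban) - p(1). L and T cancel, so b is the same in every marketplace. A retained nicotine-by-flavor term cancels too.
- Ban minus iteration 1 of Condition 1: b, b+f, b+n and b+f+n for Conditions 1 to 4, with average b + (f+n)/2.

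**3. What the factor coefficient estimates.** With balanced data and no price-by-factor term, it is the average over iterations:

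coefficient = (6 x effect with NNC on sale + 1 x effect under the ban) / 7.

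If the effect is equal in all seven iterations, all of it is recovered. If it exists only under the ban, 1/7 = 14% is recovered.

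**4. Illustration with assumed means.** Low nicotine adds 2 cigarettes and tobacco-only adds 1 while NNC is on sale; under the ban they add 8 and 6.

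| Condition | Iteration 1 | NNC eliminated | Ban effect, own reference | Versus Condition 1 iteration 1 |
|---|---|---|---|---|
| 1 | 100 | 70 | -30 | -30 |
| 2 | 101 | 76 | -25 | -24 |
| 3 | 102 | 78 | -24 | -22 |
| 4 | 103 | 84 | -19 | -16 |

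- The price main effect reports (-30 - 25 - 24 - 19)/4 = -24.5 for every marketplace.
- If the five priced iterations share iteration 1's factor effects, the nicotine coefficient is (6x2 + 8)/7 = 2.86 and the flavor coefficient is (6x1 + 6)/7 = 1.71. Together they make 4.57, against a true 8 + 6 = 14 under the ban.
- Rebuilding the Condition 4 package from the coefficients gives -24.5 + 4.57 = -19.9, against a true -16. Condition 1 would be given as -24.5, against a true -30.

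**5. Precision.**
- A same-visit ban difference removes the participant and visit random effects. Condition 1 alone has 64 such differences instead of 256, so the SE ratio is sqrt(256/64) = 2 if differences are independent across visits. With correlation r between a person's differences the ratio is 2/sqrt(1+3r); at an assumed r = 0.4 it is 2/sqrt(2.2) = 1.35.
- Factor effects within the ban iteration use one record per visit instead of seven. The SE ratio lies between 1 (all variation between visits) and sqrt(7) = 2.65 (all of it residual), while a ban-only effect is seen at full size rather than one-seventh.

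**The case against.** The strongest reply is that the plan's primary objective is the two e-liquid factors. No ban contrast is planned, so none can be biased, and the factor tests do not use iteration 1 as a reference. This is correct, and those tests remain valid as averages over iterations. But the Objectives ask a question that the average does not answer.

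Second, comparing ban with no ban inside a marketplace, with e-liquids held fixed, is a legitimate way to isolate the ban. This also stands. It answers a different question from ban plus restrictions versus today, and both should be named.

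Third, whether flavors or nicotine are needed depends on differences between conditions. Any common reference cancels from those differences, and under the written model the package contrasts are linear combinations of fitted coefficients. The cancellation is correct, so the choice of reference alone cannot hide the cost of losing flavors or nicotine. The reconstruction, however, relies on equal factor effects in all iterations, and the model has no term to test that.

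Fourth, the current-market wording is attached to cigarette settings (NNC at $0.25, no VLNC) and may not be meant to describe e-liquids. That is a fair reading, and a reason to clarify the label. Nor is Condition 1 proven to match the market, because moderate nicotine is not defined numerically. It is only the closest match available.

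**Conclusion.** The point holds as a gap between question and analysis. The written model imposes one ban effect on four marketplaces and gives the ban iteration one-seventh of the weight in each e-liquid effect. The loss ranges from none, if factor effects are the same in every iteration, to six-sevenths of the effect, if they arise only under the ban. This rests on the seven-level reading of price condition and on balanced data. If the NNC-eliminated iteration were left out of the model, the ban would not be analyzed at all in the primary outcome.

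A reader might infer more: that averaging four different iteration-1 markets biases the ban effect, by (f+n)/2 when pooled and f+n in Condition 4. With both effects set at the 0.45 for which the power section claims 80% power, that would be 0.45 and 0.90 SD. The documents do not support this. The restrictions shift the ban iterations as much as iteration 1, so under the additive model the pooled difference is (m + p(ban) + (f+n)/2) - (m + p(1) + (f+n)/2) = b, exactly the Condition 1 ban effect, with bias 0. Condition 4's own difference is also b. The gaps (f+n)/2 and f+n arise only when the target is ban plus restrictions versus today, which the SAP does not estimate. The pooled contrast departs from the Condition 1 effect only if factor effects differ between iterations.

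**What to change.** Amend the SAP and the description of the task:

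1. Add price-condition-by-nicotine and price-condition-by-flavor terms to the raw-data model, or analyze the iteration-1 and NNC-eliminated cells directly.
2. Pre-specify three sets of contrasts:
   - (a) the within-marketplace ban effect, NNC-eliminated minus own iteration 1, for each of Conditions 1 to 4;
   - (b) the flavor and nicotine effects within the NNC-eliminated iteration;
   - (c) as policy packages, each condition's NNC-eliminated iteration minus iteration 1 of Condition 1, described as the closest available match to the current market.
3. In Conditions 2 to 4, relabel iteration 1 as e-liquid restriction without a nicotine standard. State numerically what moderate and low nicotine mean.
4. Reconcile the iteration numbering: the ban is called the 6th of seven, but a current-market iteration followed by five prices would make it the 7th.

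The design already collects every cell, so the cost is wording, some extra analysis and precision: an SE up to about twice as large for a Condition 1-only ban contrast, and between 1 and 2.65 times as large for (b). For Conditions 2 to 4, the contrasts in (c) compare different visits. They no longer cancel the visit-level random effect, and they depend on the visit and carryover adjustment.

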In-Person Lab Visit 2 will be completed up to 48 hours after completing Virtual Visit 5. Participants will complete the COVID screener within 24 hours of their Lab visit via email or phone. Research staff will wear personal protective equipment during the visit including face masks and gloves. The participants will be required to wear facemasks when interacting with the staff. Temperature checks will be conducted immediately upon arrival using a thermal heat scanner.

Participants will provide CO readings be at least 6-feet away from other people, including the research staff, while they have their masks off.

Participants will be given the products they purchased during the ETM task and will be instructed to only use these products for the next seven days. They will also be given a urine collection cup and instructions for sample collection.

The field assessment validates the ETM task by having participants use the products in the real world, simulating the different regulatory environments. Actual product use enables us to measure their subjective experiences such as withdrawal, craving, or product satisfaction as well as assess changes in carbon monoxide exposure, a biomarker of harm, when using products other than menthol cigarettes. We will conduct between-subjects analyses comparing these secondary outcomes by marketplace condition.

Virtual Visit 6

Participants will complete Virtual Session 6 seven days after completing In-Person Lab Visit 2.

The following baseline assessments will be administered as an interview and entered into REDCap by the interviewer:

1. Timeline Follow Back (TLFB) Questionnaire which will assess past tobacco and nicotine product use since Virtual Visit 5.

The following surveys will be self-administered using REDCap:

1. Tobacco Policy Questionnaire
2. Minnesota Nicotine Withdrawal Scale
3. Questionnaire of Smoking Urges-Brief – Usual Brand Cigarette
4. Product Evaluation Scale – VLNC, E-Cigarette, Gum (whichever product(s) they select)
5. Perceived Health Risks Scale
6. Tobacco Product Interest Scale
7. Health Changes Questionnaire

Participants will complete the ETM task under the same marketplace condition from which they received their field assessment products. Exploratory pre-post field assessment analyses will examine how actual use of the products affects subsequent purchasing of those products.

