Research staff will conduct in-depth interviews with the participants to assess the following constructions: 1) decision-making during the ETM task; 2) use of alternative products during the field assessment; 3) product risk perceptions and; 4) opinions regarding possible tobacco control policies.

In-Person Lab Visit 3

In-Person Lab Visit 3 will be completed up to 48 hours after completing Virtual Visit 6. Participants will complete the COVID screener within 24 hours of their Lab visit via email or phone. Research staff will wear personal protective equipment during the visit including face masks and gloves. The participants will be required to wear facemasks when interacting with the staff. Temperature checks will be conducted immediately upon arrival using a thermal heat scanner. Participants will bring a first void urine sample, which will be banked for future biomarker analysis (e.g., total nicotine equivalents) and all of their used/unused products.

Participants will provide CO readings at least 6-feet away from other people, including the research staff, while they have their masks off. Participants will complete a second iteration of discrete choice task 1. Data from the two choice tasks will be compared within participants to see whether product use affected preferences.

All participants will be emailed a cessation manual and local smoking cessation resources.

Product adherence

To verify self-reported tobacco use, all used and unused products will be collected and counted at In-Person Lab Visit 3. Discrepancies between consumption stated on the TLFB versus consumption based on the products returned will be addressed. Non-adherence (i.e., using products not purchased from the ETM) will be assessed via the TLFB and qualitative interview with the importance of honest self-reporting emphasized. If participants report not using combusted tobacco, then CO readings < 6 ppm will verify their self-report.

Compensation

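### The seven-day product restriction has two different start points, and the TLFB used to judge adherence reaches back up to two days before study products are handed over

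*Combined protocol and SAP*

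**What the plan says.** Five statements in the protocol bear on the field week.

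- Virtual Visits 2-5: "Participants will be instructed to use only the products purchased from the ETM during the subsequent 7-day period after Virtual Visit 5".
- In-Person Lab Visit 2, timing: "In-Person Lab Visit 2 will be completed up to 48 hours after completing Virtual Visit 5".
- In-Person Lab Visit 2, dispensing (the period at the end of the quote is counted in days): "Participants will be given the products they purchased during the ETM task and will be instructed to only use these products for the next seven".
- Virtual Visit 6: "Participants will complete Virtual Session 6 seven days after completing In-Person Lab Visit 2". Its interview includes a "Timeline Follow Back (TLFB) Questionnaire which will assess past tobacco and nicotine product use since Virtual Visit 5".
- Product adherence: "Non-adherence (i.e., using products not purchased from the ETM) will be assessed via the TLFB and qualitative interview". No start date is attached to this definition.

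The same section has used and unused products counted at In-Person Lab Visit 3, which takes place up to 48 hours after Virtual Visit 6, and has differences between the count and the TLFB addressed. The Analysis Plan lists field product use as exploratory and analyses it by regression. Neither the visit descriptions nor the Analysis Plan gives start and end dates for the field assessment.

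**The concern.** Between Virtual Visit 5 and Lab Visit 2 participants hold none of the products to which the first instruction confines them. These are daily smokers, so many can be expected to smoke their usual brand in that interval. The TLFB at Virtual Visit 6 records those cigarettes, the adherence definition carries no date limit, and no sentence sets the interval aside.

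The field assessment is there to validate the purchasing task. If the gap days are used, someone who switched completely on receiving the products is classed as non-adherent, and cigarette use in the field week looks higher than it was. The look-back also varies in length from one participant to the next.

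Two other rules lean on the same undefined period. The purchasing-account balance is paid to participants who bought nothing and used no tobacco during the field assessment. The returned-product count is compared with a TLFB that covers different dates.

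**Working it through.** The plan states no figure for this point, so the check is day arithmetic. Set Virtual Visit 5 at day 0 and let g be the gap in days to Lab Visit 2.

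**Inputs**
- g = 0 to 2 (48-hour limit, In-Person Lab Visit 2).
- Virtual Visit 6 at day g + 7 (Virtual Visit 6).
- TLFB window: day 0 to day g + 7 (Virtual Visit 6).
- Lab Visit 3 at day g + 7 to g + 9 (In-Person Lab Visit 3).
- Entry minimum of 5 cigarettes per day (Subject Selection Criteria).

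**Window and share before hand-over**

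TLFB length = g + 7; share before hand-over = g/(g + 7).

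| g | TLFB days | Share before hand-over | Restriction from Virtual Visit 5 ends | Restriction from Lab Visit 2 ends |
|---|---|---|---|---|
| 0 | 7 | 0/7 = 0% | day 7 | day 7 |
| 1 | 8 | 1/8 = 12.5% | day 7 | day 8 |
| 2 | 9 | 2/9 = 22.2% | day 7 | day 9 |

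At g = 2 the week counted from Virtual Visit 5 has only 7 - 2 = 5 days with products in hand. It also ends two days before Virtual Visit 6.

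**Size for one participant**

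Assume usual smoking continues through a two-day gap, followed by full adherence with no cigarettes. The 10 and 20 per day rows are illustrations.

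| Usual cigarettes per day | Non-study cigarettes on TLFB | Per day over 9 days | Per day if divided by 7 |
|---|---|---|---|
| 5 | 2 x 5 = 10 | 1.1 | 1.4 |
| 10 | 2 x 10 = 20 | 2.2 | 2.9 |
| 20 | 2 x 20 = 40 | 4.4 | 5.7 |

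The true post-dispensing value in every row is 0. With g = 1 the counts halve; with g = 0 they vanish.

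**Effect on a comparison between conditions**

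Assigned products cannot affect use before they are in hand. If daily use were averaged over the whole window, a true difference d arising only after dispensing would appear as d x 7/(g + 7). At g = 2 that is 7d/9, a loss of 2/9 = 22%. If totals were analysed instead, d would be kept, but the unequal windows would add variance.

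**TLFB against product count**

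The TLFB covers day 0 to g + 7. The count covers day g to between g + 7 and g + 9. They share the seven days from Lab Visit 2 to Virtual Visit 6. The TLFB can hold up to two earlier days that the count cannot see, and the count up to two later days that the TLFB cannot see. The two can therefore disagree when every answer is truthful.

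**With the analysis window anchored at dispensing**

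Every participant contributes 7 days with products available and 0 days before hand-over.

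**The case against.** The best defence is that the plan collects more than it means to analyse. Earlier virtual visits ask about use since the previous virtual visit, so looking back to Virtual Visit 5 merely keeps the record continuous. The exploratory outcome is use during the field assessment, which is described as real-world use of the products and so can hardly begin before they are handed over. The instruction given with products in hand and the date of Virtual Visit 6 agree with each other, and the sentence under Virtual Visits 2-5 may be loose advance notice. The interview lets a participant explain cigarettes smoked before pick-up, and returned-product counts cannot contain them. No planned model uses adherence as a covariate or to exclude anyone.

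Much of this stands. A reader might infer that the plan definitely counts the gap days as field use, so that field smoking is certain to be overstated. The documents do not support that: no sentence puts those days into the product-use outcome, and the exploratory analysis does not name the TLFB as its source. A reader might also infer a biased comparison between conditions. The field condition is assigned at random, and nothing suggests that the delay to Lab Visit 2 depends on it.

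The defence does not remove the conflict. Two instructions define different weeks whenever the gap exceeds zero. The non-adherence definition, read as written over the TLFB window, catches smoking before hand-over, and no rule excludes it. That analysts could filter the days later is a reason to write the rule now, before the data are seen.

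**Conclusion.** The point holds as a conflict between stated rules that affects adherence and exploratory field outcomes. The restriction week starts at Virtual Visit 5 in one section and at Lab Visit 2 in another. The TLFB spans 7 to 9 days, of which 0 to 2 precede dispensing. The 22% share is the worst case; it is 12.5% with a one-day gap and zero when both visits fall on the same day.

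On a literal reading, usual-brand smoking in the gap is non-adherence: 10 cigarettes at the entry minimum over two days, or 40 at an assumed 20 per day, if smoking is unchanged until hand-over. Counting it as field product use is possible, because the field-assessment dates are undefined, but it is not stated.

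The primary outcome, cigarettes purchased at Virtual Visits 2-5, is untouched. The consequences are misstated levels, up to 22% dilution of a difference if use is averaged over the full window, and added noise. There is no evident directional bias between conditions. The actual distribution of the gap is not given, so the average effect cannot be computed from the documents.

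**What to change.** 1. Reconcile Virtual Visits 2-5 with In-Person Lab Visit 2 so that the field week has a single start, and state its start and end.
2. In the Analysis Plan, compute product use and adherence only from TLFB days after dispensing at Lab Visit 2, using the same number of days for every participant. Say whether the dispensing day itself counts.
3. Keep collecting the TLFB back to Virtual Visit 5 if a continuous record is wanted, but mark the days before hand-over as outside the field assessment.
4. Compare the product count with the TLFB over matching dates, for example by asking at Lab Visit 3 about use since Virtual Visit 6.
5. Apply the same defined period to the account-balance payment.

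The cost is protocol wording, a date filter and one short question at an existing visit. The filter needs no new data provided that the TLFB is stored by day; the documents do not say so explicitly, and it should be confirmed.

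### The only post-field CO reading can fall up to 48 hours after the seven-day product instruction and the use record have ended

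*Combined protocol and SAP*

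**What the plan says.** All references are to the combined protocol and SAP.

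- **Start of restriction.** In the In-Person Lab Visit 2 section, participants receive their products and "will be instructed to only use these products for the next seven days". The Virtual Visits 2-5 section counts from a different point: "Participants will be instructed to use only the products purchased from the ETM during the subsequent 7-day period after Virtual Visit 5". The two points can differ, because "In-Person Lab Visit 2 will be completed up to 48 hours after completing Virtual Visit 5".
- **End of the field period.** "Participants will complete Virtual Session 6 seven days after completing In-Person Lab Visit 2". The TLFB given there is the one "which will assess past tobacco and nicotine product use since Virtual Visit 5". The qualitative interview is also at this visit.
- **Post-field measures.** "In-Person Lab Visit 3 will be completed up to 48 hours after completing Virtual Visit 6". CO is read, urine is handed over and products are counted at that visit. No TLFB or question about the last cigarette is listed.
- **Use of CO.** The Lab Visit 2 section names change in CO among the measures the field assessment makes possible, to be compared by marketplace condition. The Product adherence section adds: "If participants report not using combusted tobacco, then CO readings < 6 ppm will verify their self-report".
- **Payment.** For participants who buy nothing and use no tobacco in the field period, "then they will receive their ETM account balance at Virtual Visit 6".
- **Analysis.** Under Analysis of Exploratory Outcomes, field biomarkers are regressed on the condition factors and the baseline value. There is no term for time since Virtual Visit 6.

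**The concern.** The instruction, the use record and the CO reading should describe the same days. As scheduled, the first two stop at Virtual Visit 6 and the third can come two days later. In between, participants are under no stated instruction to avoid their usual brand, and no scheduled question asks whether they smoked it.

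The documents make some resumption plausible. Participants are daily smokers who are not seeking treatment to quit. The account balance is sized to about seven days of cigarette spending, so products may run out around Virtual Visit 6. The risk section anticipates a return to the usual brand at the end of the study. The Background reports that more than 75% of participants assigned to very low nicotine cigarettes used at least one non-study cigarette in trials of six weeks or longer, despite instructions not to. That setting differs from this one, so the figure gives a direction, not an estimate.

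Two uses of CO are at stake: the exploratory comparison by condition, and the verification of reports of no combusted use. In the second, a reading at Lab Visit 3 is set against a self-report that closed at Virtual Visit 6.

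**Working it through.** The plan gives no figure to reproduce. The check is a timeline followed by a decay illustration.

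**Timeline, in hours from Virtual Visit 5.** Let a be the delay to Lab Visit 2 (0 to 48) and b the delay from Virtual Visit 6 to Lab Visit 3 (0 to 48). Both ranges come from the visit sections.

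- Lab Visit 2 is at a, Virtual Visit 6 at a + 168, and Lab Visit 3 at a + 168 + b.
- TLFB coverage runs from 0 to a + 168, so the unrecorded gap before CO is b, or 0 to 48 h.
- Counted from Lab Visit 2, the restriction ends at a + 168. The unrestricted gap is b, or 0 to 48 h.
- Counted from Virtual Visit 5, the restriction ends at 168. The unrestricted gap is a + b, or 0 to 96 h. Its first a hours fall before Virtual Visit 6 and are covered by the TLFB; its last b hours are not.
- At b = 48, the time from Lab Visit 2 to Lab Visit 3 is 168 + 48 = 216 h, and 48/216 = 22% of it has neither a restriction nor a use record. At b = 24 the share is 24/192 = 12.5%. At b = 0 it is zero.

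**How much of the Virtual Visit 6 CO level is still there.** Share remaining = 2^(-t/h). The half-life h is an assumption (2 to 8 h), since the documents give none.

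| h | t = 12 h | t = 24 h | t = 48 h |
|---|---|---|---|
| 2 h | 1.6% | 0.02% | <0.01% |
| 4 h | 12.5% | 1.6% | 0.02% |
| 8 h | 35.4% | 12.5% | 1.6% |

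After a day or more, the reading is almost entirely set by smoking since Virtual Visit 6. This shows which period the reading describes. It does not show that behavior changed in that period.

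**Whether the product count fills the gap.** The count at Lab Visit 3 covers study products only, so it cannot detect usual-brand smoking. It also runs b hours longer than the TLFB. Study products used after Virtual Visit 6 would therefore look like a discrepancy with a correct TLFB.

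**The case against.** Several points on the other side stand.

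- 48 hours is an upper limit, and a same-day Lab Visit 3 leaves no gap after Virtual Visit 6.
- Participants are told that adherence will be assessed at Lab Visit 3. This may deter some from resuming, although it does not lengthen the seven days.
- The field assessment is there to validate the marketplace task, and CO is only one of its measures. Withdrawal, craving and product evaluation are collected at Virtual Visit 6, with no gap.
- The Analysis Plan lists field biomarkers as exploratory, although the Lab Visit 2 section calls the field outcomes secondary.

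A reader might infer more than the documents support.

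- **That the urine biomarkers are equally affected.** The sample is brought to Lab Visit 3, but the day of the void is not stated, and the collection instructions handed out at Lab Visit 2 are not in the documents. Urine shares the problem only if it is voided after Virtual Visit 6.
- **That a difference between conditions will be hidden.** If a fraction f in each group resumed fully and independently of condition, the contrast would shrink by about f. But f is unknown, and those conditions are assumptions. Very low nicotine cigarettes are also smoked, so buyers who return to their usual brand may show little change in CO.
- **That truthful abstainers will be failed.** The plan states no consequence for a reading of 6 ppm or more. A conflict would also need an abstainer to resume within the gap.
- **That the incentive lapses for everyone.** The delayed balance concerns only participants who bought nothing and used no tobacco, a group of unstated size.

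**Conclusion.** The point holds for CO. Followed as written, the schedule allows up to 48 hours between the end of both the Lab Visit 2 instruction and the TLFB and the only post-field CO reading. If the seven days are counted from Virtual Visit 5, the unrestricted time before that reading is up to 96 hours. When the gap after Virtual Visit 6 is a day or more, the CO comparison and the 6 ppm check can describe unrestricted, unrecorded use rather than the field week. This rests on the assumed half-life of 2 to 8 hours. The resulting bias cannot be sized from the documents, because neither the distribution of the gap nor the proportion resuming is given.

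The consequence is limited to an exploratory outcome and the adherence check. Cigarettes purchased at Virtual Visits 2-5, the primary outcome, are not touched. The change is still worth making before data collection, because use in the gap cannot be reliably recovered afterwards.

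**What to change.** 1. Reconcile the Virtual Visits 2-5, Lab Visit 2, Virtual Visit 6 and Lab Visit 3 sections so that the product instruction, the use record and the biosamples cover the same stated period.
2. Schedule Lab Visit 3 on the same day as Virtual Visit 6 where possible.
3. Where it is not possible, extend the TLFB to Lab Visit 3 and record the hours since Virtual Visit 6 and the time of the last cigarette. Use these in the CO model and when applying the 6 ppm check, and compare the product count with the TLFB over the same dates.
4. State in the protocol that the first-void urine is collected on the morning of Virtual Visit 6. If the collection instructions already say so, this only makes it visible.
5. Release the non-buyer balance after the Lab Visit 3 CO reading.

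The cost is less flexible booking, a few extra minutes of interview and a slightly later payment for non-buyers. Simply lengthening the product restriction to Lab Visit 3 would be less clean: the account balance is sized to about seven days, and a supply stretched by up to two days could itself produce non-adherence.
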